#### **1. Primary End Points:**

There are two aspects to the primary end points of the study and as follows:

- 1) To value the efficacies of LNG-IUS as fertility-preserving treatment for early EC and EAH by pathologic response. Pathologic response to medicine treatment is categorized as complete response (CR), partial response (PR), no change (NC), and progressive disease (PD). CR is defined as the absence of any hyperplastic or cancerous lesion. PR is defined as the residual lesion with degeneration and atrophy of endometrial glands. NC is defined as residual lesion without degeneration or atrophy of endometrial glands. PD is defined as the appearance of endometrial cancer for EAH and grade 2 (G2) or 3 for EC.
- 2) To compare the rate of pregnancy and alive baby delivery.

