**Comments:**

(1) The basic history collection includes detailed history of prior treatment; with or without contraindications of oral highly active progestogens: hypertension, diabetes (DM), liver function damage, thrombotic disease and so on; with or without reproductive endocrine disease: infertility, PCO syndrome, insulin resistance (IR), impaired fasting glucose (IFG) and so on; with or without any other system disease; surgical history, allergy history; family history especially for carcinomas.

(2) The basic endocrine examinations include sex hormone, anti mullerian hormone (AMH), and insulin release test (IRT) to rule out PCO syndrome, IR, IFG, and DM. Follow-up treatment will be provided when necessary.

(3) If the patients have abnormality in breast ultrasound, she needs to visit the Department of Breast Surgery to evaluate the risk of continuous progesterone treatment.

(4) Based on the inclusion and exclusion criteria of this study, the patients are allocated to one of the arms by central randomization with study site allocation. The arms and interventions and the probability of distribution are as follows:

1) If the patients does not have thromboembolism, liver dysfunction, hypertension, or diabetes, she will be assigned to one of the following two groups, with a probability of 50%, respectively: a) sequential oral medroxyprogesterone acetate (MPA) 500mg QD group; and b) LNG-IUS (Mirena®) group.

2) If the patients are diagnosed of thromboembolism, liver dysfunction, hypertension, or diabetes, she will be assigned to one of the following two groups, with a probability of 50%, respectively: a) intramuscular injection of leuporelin acetate microspheres (GnRH-a) + LNG-IUS group; and b) LNG-IUS (Mirena®) group.

(5) For the groups of oral highly active progestogens, medicine treatment should only be continued if the liver function is normal, which is evaluated by monthly tests.

(6) For the groups of LNG-IUS, the medical device needs to be replaced by a new one on every hysteroscopy to insure adequate drug release

(7) Endometrial tissue sampling for diagnosis should be performed by hysteroscopy every 3 months, and the histologic diagnoses of all specimens are made by two categorized pathologists.

[figure not shown]

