(8) After 6 months' continuous progestogen-based therapy, if the patients has PR/NC, progestogen-based therapy should be continued for one more cycle (3 months), and if the patient still has PR/NC, she will withdraw from this trial and undergo hysterectomy; if the patients has CR at the second or third endometrial evaluation, fertility treatment will be initiated immediately; and if the patients has documented progression on the biopsies at any time, the protocol treatment will be stopped and hysterectomy be recommended.

(9) The option of natural conception or assisted reproduction should be discussed with the fertility specialist in the reproduction center of our hospital; assisted reproduction is recommended if the patients 1) has history of infertility; 2) has risk factors for infertility such as PCO syndrome, obesity, diabetes, and lack of ovulation; or 3) suffers from failed pregnancies after 6 months of natural conception.

- (10) If the patient succeeds in conceiving, she will receive professional prenatal examinations from the obstetrics specialist in our hospital.
- (11) All the professors in the Department of Obstetrics and Reproductive Center of our hospital are on this research team.
- (12) Long-term follow-up will proceed even after treatments are finished, and corresponding clinical treatments will be provided for patients with different conditions.

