### **III. Statistical Analysis Plan**

#### **1. The Sample Size Calculation:**

This clinical study is a RCT and aims to evaluate the fertility-preserving treatments for young women having EAH and EC. Experimental stratification is conducted based on whether the participants have contraindications of oral highly active progesterone (including thromboembolic disease, liver dysfunction, hypertension, and diabetes). The distribution ratio between the experimental group and the control group is 1:1. The estimated sample size can detect difference under  $\alpha = 0.05$  and Power = 0.8, calculating the exact sample size and randomizing grouping. For EC without contraindications of oral highly active progestogens, we will compare sample rates among the three groups by using the PASS software and will calculate the sample size of 18 cases for each group. For EC with contraindications of oral highly active progestogens, we will compare sample rates between the two groups by using the PASS software and will calculate the sample size of 30 cases for each group. Similarly, the calculation of sample size for patients having EAH with and without contraindications of oral highly active progestogens are 14 and 20 cases for each group.

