Clinically, Mirena® LNG-IUS is one of the most widely used Levonorgestrel-releasing intrauterine devices, which is produced by Bayer Health Care Pharmaceutical Inc., Wayne, NY. Mirena®, the progestogen device, has high contraceptive effectiveness. Each Mirena contains 52 mg of levonorgestrel. Its in vivo drug rate during the first five-year period is approximately 20 ug /day and will reduce to 11 ug/day in five years. The hormone released from the IUS causes significant local effect characterized by glandular atrophy and stromal decidualization. This dominant suppressive effect of the endometrium is seen through the overall thickness of the arterial walls with capillary thrombosis. The end result is that the suppression of endometrial tissue growth becomes insensitive to estradiol. The LNG-IUS has an important role in the disease prevention or treatment of uterine pathologies, such as endometrial polyps, endometrial cancer, and tamoxifen-induced changes[18]. Compared with oral progestogens, LNG-IUS can elevate the local drug concentration and act on the PgRs in the endometrium directly, which generates a much higher concentration of progesterone in the endometrial mucosa[17]. LNG-IUS may still be a useful treatment option, especially because it has fewer and milder systemic side-effects such as weight gain and liver damage[6]. Some studies suggest that LNG-IUS is superior to oral progestogens in the fertility-preserving treatment of EAH and EC. Gallos et al[19] reported in a systemic review that LNG-IUS achieved a higher pooled regression rate than oral progestogens for EAH (90 vs 69%,  $P = 0.03$ ).

A higher regression was also seen in a randomized, multicenter study carried out by Orbo et al[20]. This is similar to findings of some studies and systemic reviews[17, 21]

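### Is the stated power of 0.8 wrong because the sample-size section gives no rates, and the background rates of 90 vs 69% would give only about 0.4 to 0.5 at 20 per group?

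*Combined protocol and SAP*

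**What the plan says.** Section III.1 (The Sample Size Calculation) gives alpha 0.05 and "Power = 0.8, calculating the exact sample size and randomizing grouping", once, for all strata. For the two-arm cancer stratum it explains that "we will compare sample rates between the two groups by using the PASS software", and it describes the three-arm stratum in the same way. The sizes are 18 per group (cancer, no contraindications to oral progestogens, three arms), 30 per group (cancer, with contraindications), and, for hyperplasia, "EAH with and without contraindications of oral highly active progestogens are 14 and 20 cases for each group".

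Section I.1 (Primary End Points) has two aspects. One is pathologic response, which separates complete from partial response. The other is "To compare the rate of pregnancy and alive baby delivery". Section III.3 (Statistics) plans survival analysis for the primary end points and names no test.

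The only comparative rates in the documents are in section V (Research Status and Development Trend). A systematic review is cited there as finding that "LNG-IUS achieved a higher pooled regression rate than oral progestogens for EAH (90 vs 69" per cent). Under section II.3.1, Comments (4), hyperplasia patients without contraindications are randomised between "sequential oral medroxyprogesterone acetate (MPA) 500mg QD group; and b) LNG-IUS", which is the same kind of contrast. Comments (7) says "Endometrial tissue sampling for diagnosis should be performed by hysteroscopy every 3 months", and Comments (8) says "if the patients has CR at the second or third endometrial evaluation, fertility treatment will be initiated immediately".

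**The concern.** A power of 0.8 means nothing until one says for what difference, on which end point and by which test. None of these is given, and the sizing is on rates while the primary analysis is a survival analysis.

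The one pair of rates that a reader can find matches the arms of the 20-per-group stratum, so it is natural to put it in. The power then comes out at about half of what is claimed. If complete response was the sizing end point and the cited effect were true, that comparison would miss it in roughly 5 to 6 trials out of 10 (chi-square or log-rank, two-sided), against the 2 in 10 that power of 0.8 implies. A null result could then be misread as equivalence of the two treatments.

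**Working it through.** **The plan's own figure.** The 20 per group cannot be reproduced, because section III.1 gives no rates. What can be computed is the power at rates borrowed from section V.

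**Inputs.** n = 20 per group, 1:1, alpha 0.05 (section III.1); p1 = 0.90 and p2 = 0.69 (section V). Assumed: regression means complete response, the rates apply at 9 months, the test is two-sided and nobody drops out.

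**Comparison of rates, pooled formula.** Mean rate (0.90 + 0.69)/2 = 0.795.
- Null term: √(2 × 0.795 × 0.205) = 0.571
- Alternative term: √(0.90 × 0.10 + 0.69 × 0.31) = √0.3039 = 0.551
- Power = Φ[(0.21 × √20 − 1.960 × 0.571)/0.551] = Φ(−0.326) = 0.37
- n for 0.8 = (1.960 × 0.571 + 0.842 × 0.551)² / 0.21² = 56.8, so 57 per group

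**Enumeration of all outcomes at 20 per group.**

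| Test | Two-sided | One-sided |
|---|---|---|
| Uncorrected chi-square | 0.383 | 0.517 |
| Fisher | 0.264 | 0.369 |

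By the uncorrected chi-square, two-sided, 54 per group gives 0.797 and 55 gives 0.805.

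**Log-rank (assumed test), proportional hazards.**
- HR = ln(0.10)/ln(0.31) = 1.966, and ln HR = 0.676
- Events = 20 × (0.90 + 0.69) = 31.8
- Power = Φ(0.676 × √(31.8/4) − 1.960) = Φ(−0.054) = 0.48 two-sided, or 0.60 one-sided
- Events for 0.8 = 4 × (1.960 + 0.842)²/0.676² = 68.7, and 68.7/1.59 = 43.2 per group

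Simulation gives 0.46 with biopsies at 3, 6 and 9 months, and 0.43 if response counts only at 6 and 9 months. It gives 0.40 to 0.41 if, in addition, 80 to 90% of the hazard falls before month 6.

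So at 90 vs 69% no variant reaches 0.8. The next question is whether 20 per group is wrong.

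**Reverse check.** By the uncorrected chi-square, two-sided, 20 per group has power 0.803 for 52 vs 90%. The claim of 0.8 is therefore attainable, for a difference of 90 − 52 = 38 points instead of the cited 90 − 69 = 21. Section III.1 does not say which was meant.

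**Other strata.** The documents give no rates for 14, 18 or 30 per group on any end point. If the sizing end point was pregnancy or live birth, the 90 vs 69% does not apply to the 20 per group either.

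**Would a table of detectable differences help?** Its entries depend on choices that the plan does not make:

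| Configuration | Uncorrected chi-square | Fisher |
|---|---|---|
| 14/group, 50 vs 94% | 0.808 | 0.675 |
| 20/group, 52 vs 90% | 0.803 | 0.697 |
| 30/group, 59 vs 90% | 0.818 | 0.733 |

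For three arms of 18, the global chi-square has power 0.81 at 50/50/90% but 0.68 at 50/70/90%, with the same extremes. All these entries compare rates, whereas section III.3 plans survival analysis. Entries for pregnancy or live birth would need base rates that the documents do not contain.

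**The case for a change.** The best case for a change is that the omission is certain from the text. A PASS run needs assumed rates, so they existed and could be printed. The plan calls itself a randomised trial and claims a power, so the claim ought to be checkable. The cost would be a few lines of wording, and readers would learn that 20 per group suits a gap of about 38 points, far above the 21 points quoted in the background.

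Much of this stands. The inputs are missing, the sizing and the planned analysis are not linked, and the conditional figures are right. What does not stand is the step to a defect that alters the trial. The 90 vs 69% is one line in a literature summary. It is a pooled regression rate, and the documents do not say whether regression means complete response, when it was measured or with which oral progestogen. It bears on one stratum of four. A table worked out afterwards would not recover the design assumption, and its entries move by about 0.09 to 0.13 with the choice of test alone. The group sizes themselves are stated, so allocation does not wait on the missing inputs. The introduction also calls this a phase II study, so modest groups are not in themselves a fault.

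**Conclusion.** No change to the plan follows. The sample-size section is incompletely documented, but no stated figure is shown to be wrong: 20 per group delivers 0.80 at 52 vs 90% and about 0.38 at 90 vs 69% (uncorrected chi-square, two-sided), and the plan commits to neither.

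As a conditional illustration, if the background rates were complete-response rates with no dropout, two-sided power would be 0.26 (Fisher), 0.38 (chi-square) or about 0.40 to 0.48 (log-rank). The most favourable reading, one-sided log-rank, gives about 0.60. For 14, 18 and 30 per group, and for pregnancy or live birth in any stratum, nothing can be checked.

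The missing inputs enter no analysis. Stating them would leave group sizes, randomisation, test results and decisions as they are. Analysts can name the survival test and give confidence intervals when they report, as is usual, and those intervals will show what each stratum can and cannot rule out. The practical caution is for the reader: the 0.8 should not be used to treat a non-significant stratum result as evidence of equivalence.

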#### **2. Random Allocation Method:**

Eligible participants will be screened according to the inclusion and exclusion criteria. They will be numbered in order of admission, and the random numbers are generated based on the random number table. Then the participants are randomly assigned and given appropriate treatment.

#### **3. Statistics:**

SPSS software will be used for statistical analysis. Survival analysis is used for primary end points and chi-square test for secondary end points.

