**2.3 Conditions for Withdrawal from the Treatment (meeting any one of the following conditions)**

- (1) The participants volunteer to withdraw from the trial;
- (2) If the participants have PD on the histologic diagnosis; if the participants have PR and NC after 6 to 9 months of progestogen-based therapy; and if the participants have recurrence of disease while preparing for or during pregnancy;
- (3) If the participants cannot tolerate adverse drug reaction and are judged unfit for medical treatment by the clinician-in-charge.

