## **V. Research Status and Development Trend**

Endometrial carcinoma (EC) is the most common gynecology cancer worldwide, and is usually characterized by well-differentiated (grade 1 [G1]) and early stage (according to International Federation of Obstetrics and Gynecology [FIGO] staging system--stage IA), which contributed to a very high cure rate with standard treatment.[14, 15] Atypical endometrial hyperplasia (EAH) suggests a preliminary state with progression to EC, and tends to occur in young women. [1, 6-8] For these young patients, conventional treatment using hysterectomy affects their quality of life immensely because it deprives them of any chance to bear a child. If the patients have a strong wish to preserve their fertility, the fertility-preserving treatment can be considered. In China, as lifestyle and diet both change, the incidence of EC has been increasing very rapidly,[5, 14] and the need for fertility-preserving treatment is also on the rise.

The efficacy and safety of oral progestogens as fertility-preserving therapy in patients with EAH and EC has been reported in many studies. For instance, the first report was conducted by Kelley and Baker in 1961[16]. Oral progestogens function by inhibiting the estrogen receptor, leading to a decrease in endometrial cell mitosis, promotion of apoptosis, and production of secretory endometrium[17]. However, the highly active progestogens often have many and severe side-effects like gastrointestinal reaction, insomnia, nervousness, dizziness, coagulation, liver and

kidney dysfunction, and weight gain etc. In addition, these patients always have complications such as obesity, hypertension, and impaired glucose metabolism, which often make the patients withdraw from therapy. Therefore, an effective and safe conservative treatment is urgently needed for young patients having EAH and EC who wish to preserve their fertility but cannot tolerate the highly active progestogen treatment. It has become increasingly important and necessary to find a safe and effective fertility-preserving treatment with better tolerability, and fewer and milder side effects.

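### Survival analysis is named for pregnancy and live birth with no rule for women who have a hysterectomy; if they are censored, both rates are too high and a response-driven difference between arms shrinks

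*Combined protocol and SAP*

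**What the plan says.** Section I, Primary End Points, names two aspects: pathologic response, and a comparison of pregnancy and live-birth rates. The analysis is in section III.3 (Statistics), which has two sentences: "SPSS software will be used for statistical analysis" and "Survival analysis is used for primary end points and chi-square test for secondary end points".

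What happens to non-responders is in the Comments under the two treatment schedules (EAH item 8, EC item 11). After six months, a woman with partial response or no change has one more three-month cycle. If the lesion persists, "she will withdraw from this trial and undergo hysterectomy". For responders, "if the patients has CR at the second or third endometrial evaluation, fertility treatment will be initiated immediately". Progression at any time stops treatment, and hysterectomy is recommended.

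Section II.2.3 is headed "Conditions for Withdrawal from the Treatment". Besides progression, voluntary withdrawal and intolerance, it lists persistent lesions: "if the participants have PR and NC after 6 to 9 months of progestogen-based therapy". A further listed condition falls in the fertility phase: "if the participants have recurrence of disease while preparing for or during pregnancy". Comments item 12 (EAH) and item 15 (EC) promise long-term follow-up after treatment, with no duration. Section V says of hysterectomy that "it deprives them of any chance to bear a child".

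**The concern.** A censored woman is assumed to have the same future chance of the event as those still at risk. A woman without a uterus has none, so for pregnancy and birth hysterectomy is a competing event. Section III.3 does not address this. A woman recorded as withdrawn from the trial would ordinarily enter a Kaplan-Meier or log-rank analysis as censored.

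Three things would follow:

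- The pregnancy and birth rates would describe women who responded, whereas section I asks for them by treatment group.
- Every arm with non-responders would have rates that are too high, and the arm with the poorest response would gain most.
- A true difference that arises because one treatment clears more lesions would be largely removed.

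Complete response is open to a related error if women who progress are censored.

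**Working it through.** **Plan's own figure.** The documents state no pregnancy rate, birth rate, event count or censoring fraction, so there is none to reproduce. The group sizes in III.1 (18, 30, 14 and 20) cannot be rebuilt because no event rates are given. The point does not depend on them.

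**Inputs.**
- From the Comments: conception efforts start after complete response (CR) at month 6 or 9, and the last non-responders leave at month 9.
- From section V: 90% against 69%, a background pooled regression rate for EAH (LNG-IUS against oral progestogens) with no time point. I assume these are CR by month 9.
- Assumed: CR by month 6 of 70% and 50%; equal monthly conception rate L = 0.04 to 0.08 after CR in both arms; horizon H of 12 or 18 months from randomisation.

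**Pregnancy.** Let p6 and p9 be CR by months 6 and 9.

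True rate per randomised woman = p6[1 − exp(−L(H−6))] + (p9 − p6)[1 − exp(−L(H−9))].

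Before month 9 everyone is in the risk set; after it only responders are. With non-responders censored at month 9, Kaplan-Meier rate = 1 − [1 − p6(1 − exp(−3L))] × exp(−L(H−9)).

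Worked case, L = 0.04, H = 12:
- 90% arm, true: 0.70 × 0.2134 + 0.20 × 0.1131 = 0.172. Kaplan-Meier: 1 − (1 − 0.70 × 0.1131) × 0.8869 = 0.183.
- 69% arm, true: 0.50 × 0.2134 + 0.19 × 0.1131 = 0.128. Kaplan-Meier: 1 − (1 − 0.50 × 0.1131) × 0.8869 = 0.163.

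| H | L | True, 90% / 69% arm | Kaplan-Meier, 90% / 69% arm | True gap | Kaplan-Meier gap | Excess, 90% / 69% arm |
|---|---|---|---|---|---|---|
| 12 | 0.04 | 17.2 / 12.8 | 18.3 / 16.3 | 4.4 | 2.0 | 1.1 / 3.5 |
| 12 | 0.08 | 31.0 / 23.1 | 33.1 / 29.7 | 7.8 | 3.4 | 2.1 / 6.6 |
| 18 | 0.04 | 32.7 / 24.8 | 35.8 / 34.2 | 7.9 | 1.6 | 3.0 / 9.4 |
| 18 | 0.08 | 53.5 / 40.6 | 58.6 / 56.5 | 12.9 | 2.1 | 5.1 / 15.9 |

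Rates are percentages; gaps and excesses are percentage points, taken before rounding.

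With equal response (62% by month 6 and 80% by month 9 in both arms) there is no gap to distort, but each arm is still overstated by 2.3-4.3 points at 12 months and 6.0-10.3 at 18.

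**Live birth.** If conception follows CR, a birth before month 9 would need a gestation under three months. The curve is therefore flat until the last non-responders have gone, and then follows responders only: Kaplan-Meier rate = true rate / p9. The inflation is 1/0.90 = 1.11, 1/0.80 = 1.25 and 1/0.69 = 1.45. This requires that nobody is censored for recurrence after CR. If such women are censored, the inflation is larger and changes with follow-up.

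**Complete response.** Assume a 35% chance of CR at each of three evaluations. With women who progress censored, Kaplan-Meier gives 1 − 0.65³ = 72.5%. If a share d progresses at each evaluation, the true figure is 0.35[1 + (0.65 − d) + (0.65 − d)²]: 70.9%, 68.6% and 64.8% for d = 2%, 5% and 10%. The excess is 1.6, 3.9 and 7.7 points.

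**Power.** In simulated log-rank tests for pregnancy with 20 per group (the size for EAH without contraindications) under the 90% / 69% assumptions, power at 12-18 months was 7-13% with non-responders kept in the risk set and 5-6% with them censored.

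**The case against.** The strongest reply is that the plan never says these women are censored. It speaks of rates, sizes the trial by comparing rates, and promises long-term follow-up. Counting women after hysterectomy as not pregnant is equally compatible with the text, and then no bias arises. This stands: the fault is a missing rule whose usual default is biased. A reader might infer that the planned analysis is already wrong; the documents do not support that.

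The sizes are also open to challenge. Conception rates, month-6 response and horizon are assumed. Both the trial and its recruitment are placed in January 2018 to December 2020. With even accrual cut at that date, 12/36 of women would reach 24 months and 3/36 would reach 33, so the larger figures that long horizons give are not used here. At 12 months an excess of 6.6 points is about 1.3 women in 20, less than the sampling error of one arm's rate. This too stands, but a systematic excess does not average out.

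Three stronger readings are tempting:

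- That II.2.3 lets non-responders leave at month 6 and so biases CR. If all continue to month 9, there is no such bias. If all leave at month 6, the curve stops at its month-6 value (1 − 0.65² = 57.8% in the example above), which is then also the true figure. Only a mixture would bias it, and the documents describe none.
- That the live-birth inflation is the same at any follow-up. Recurrence before or during pregnancy is a listed withdrawal condition, so this holds only if those women are not censored.
- That the comparison would change sign. That needs a further assumed difference in conception after CR.

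**Conclusion.** The concern holds as a conditional one. Section III.3 leaves open how women who have a hysterectomy count towards pregnancy and live birth, and the ordinary default would give rates among responders. Once these women are censored the direction is firm: rates too high wherever there are non-responders, most so where response is poorest, and a response-driven gap reduced. The sizes are illustrations only. Because power is low under either handling, the damage is mainly to the reported primary rates and not to the test result. Censoring progression would likewise overstate CR. I rate this as should-fix.

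**What to change.** In III.3:

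1. Analyse pregnancy and live birth separately, from randomisation, in all randomised women within each stratum. State the horizon and a planned end of follow-up. Use cumulative incidence with hysterectomy as a competing event, compared by Gray's test. In SPSS, the alternative is to keep women after hysterectomy event-free in the risk set to their own planned end of follow-up; the two are equivalent only where all censoring is administrative. Censor only at administrative end or true loss to follow-up. Stopping treatment, progression or recurrence without hysterectomy does not end follow-up.
2. Analyse CR by month 9 as a proportion of all randomised women. Count progression, persistent partial response or no change, and withdrawal for any reason without documented CR (including intolerance and voluntary withdrawal) as no CR. Add a sensitivity analysis for women administratively cut off before month 9.
3. Reconcile II.2.3 (withdrawal from treatment) with Comments items 8 and 11 (withdrawal from the trial) and items 12 and 15 (long-term follow-up), so that outcome follow-up continues after treatment stops. No clinical rule is proposed.

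The cost is a few sentences in the SAP, one protocol clarification, and simple outcome follow-up of withdrawn women (date of hysterectomy, any pregnancy or birth). Gray's test may need a second package; the risk-set version does not. Reported rates will be lower than Kaplan-Meier rates, and power at the planned sizes stays low.

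### The pregnancy and live-birth analysis names no baseline adjustment, although age and infertility history are known before randomisation and not balanced by design; two fixed covariates would give a small, cheap gain

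*Combined protocol and SAP*

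**What the plan says.** - **End point.** Section I, Primary End Points, item 2: "To compare the rate of pregnancy and alive baby delivery".
- **Analysis.** The whole of section III.3 on method for the primary end points is "Survival analysis is used for primary end points". No model, covariate, time origin, censoring rule or analysis set is given.
- **Infertility history.** History collection in comment (1), worded alike for EAH (II.3.1) and EC (II.3.2), covers "with or without reproductive endocrine disease: infertility, PCO syndrome, insulin resistance (IR), impaired fasting glucose (IFG) and so on". Tables 1 and 2 place it at pre-screening (month -1), before random assignment (month 0).
- **Age.** It must be known to apply the limit of 40 years in inclusion criterion (1) for each disease.
- **Relevance to conception.** II.3.1 comment (9), repeated in II.3.2 comment (12): "assisted reproduction is recommended if the patients 1) has history of infertility". The documents do not say how strongly infertility history predicts pregnancy, and they state no link between age and pregnancy.
- **Balancing.** III.1: "Experimental stratification is conducted based on whether the participants have contraindications of oral highly active progesterone". EAH and EC are allocated separately, which makes four strata. III.2 adds that "the random numbers are generated based on the random number table". Neither section mentions balancing on age or infertility history.

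**The concern.** The protocol itself treats infertility history as relevant to how a woman tries to conceive, and it records that history before allocation. Nothing in the randomisation balances it, so only the analysis can take account of it, and the analysis section is silent. In groups this small, a difference in pregnancy rates could partly reflect which arm happened to receive more women with prior infertility. Leaving a prognostic factor out of a Cox model also pulls the estimated treatment effect towards no difference, which lowers power. If covariates are instead chosen after the results are seen, the choice itself becomes open to question.

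**Working it through.** **1. The plan's own figures.** III.1 gives α = 0.05, power 0.8 and group sizes of 18 (EC without contraindications, three groups), 30 (EC with, two groups), 14 (EAH with, two groups) and 20 (EAH without, two groups). Total: 3×18 + 2×30 + 2×14 + 2×20 = 54 + 60 + 28 + 40 = 182. The sizes cannot be reproduced, because no rates, effect size or sidedness are stated. The only comparative rates quoted (section V) are 90% and 69%. They concern EAH regression, not pregnancy, and would need 57 per group (two-sided, no continuity correction), not 20.

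**2. Chance imbalance.** Assume a yes/no factor held by half the women. The difference in counts between two groups of n has SD √(n/2). With k the smallest count difference that reaches 20 points, P ≈ 2[1 − Φ((k − 0.5)/√(n/2))]. Exact binomial values are beside it. For age, the standardised difference between two groups has SD √(2/n).

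| n per group | k | (k − 0.5)/√(n/2) | P(gap ≥ 20 points), exact | SD of age difference | P(age gap > 0.5 SD) |
|---|---|---|---|---|---|
| 14 | 3 | 2.5/2.65 = 0.94 | 34% | 0.38 | 19% |
| 18 | 4 | 3.5/3.00 = 1.17 | 24% | 0.33 | 13% |
| 20 | 4 | 3.5/3.16 = 1.11 | 27% | 0.32 | 11% |
| 30 | 6 | 5.5/3.87 = 1.42 | 16% (15.5%) | 0.26 | 5% |

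The rise from 18 to 20 is discreteness: four women are needed in both cases. At 40% prevalence the imbalance figures are 34, 23, 26 and 15%.

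**3. Validity.** Imbalance of this kind is already allowed for in the sampling distribution of a randomised comparison. With no treatment effect and moderate covariates (hazard ratio 0.65 per SD of age, 0.5 for infertility), simulated single-stratum Cox models rejected in 2.8–4.0% of runs unadjusted and 4.5–5.2% adjusted, at 14, 20 and 30 per group. In the stratified model of step 4, type I error did not exceed about 0.06 in any contrast.

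**4. Power of the proposed model.** Simulation of all 182 women: four strata, treatment terms within stratum, shared age and infertility covariates, treatment hazard ratio 2, infertility prevalence 50%, 1,000 runs per setting. Apart from the 182 women and four strata, all of these are assumptions. Ranges run over the contrasts.

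| Reference-arm pregnancy | Infertility HR; age HR per SD | Unadjusted | Adjusted |
|---|---|---|---|
| 35% | 0.5; 0.75 | 0.13–0.33 | 0.15–0.34 |
| 35% | 0.4; 0.65 | 0.11–0.26 | 0.12–0.32 |
| 55% | 0.5; 0.75 | 0.23–0.44 | 0.26–0.50 |
| 55% | 0.4; 0.65 | 0.18–0.38 | 0.22–0.48 |

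With weak covariates (0.8; 0.9) single contrasts gain about 0–2 points. Averaged over contrasts, the gain is about 0–1 points (weak), 2–4 (moderate) and 4–5 (strong). With no covariate effect, power changes by at most 1 point. The simulation error of one power value near 0.3 is √(0.3×0.7/1000) = 0.014, so these averages are good to a point or two.

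**5. Sensitivity to larger effects.** Separate Cox models per two-group comparison were also simulated, with treatment hazard ratios of 2.5 to 4, infertility prevalence 40% and control pregnancy 20% or 35%. The gains were 1–3 points (age 0.8, infertility 0.7), 3–9 (0.65, 0.5) and 9–18 (0.5, 0.35). The direction is the same. The size depends on treatment and covariate effects that the documents do not supply.

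**The case against.** **Survival analysis may already include an adjusted Cox model.** This stands in part. A reader might infer that the plan has decided to ignore age and infertility, but III.3 is silent and does not exclude them. What can be said is that no covariate is prespecified.

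**The link to pregnancy is not shown.** This stands. A reader might infer that both factors are strongly tied to the outcome. The documents support this only qualitatively for infertility and not at all for age. The assisted-reproduction rule could also weaken, or even reverse, the association between infertility history and time to pregnancy. In addition, diabetes, one of the infertility risk factors listed there, is already part of the contraindication stratum.

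**Adjustment could recover the power the trial lacks.** A reader might infer this by pooling MPA against LNG-IUS over both diseases (18 + 20 = 38 per arm), where simulated power rises from 0.56 to 0.62 or from 0.50 to 0.60. The plan sizes each stratum separately and foresees no pooled contrast. Those runs also assume 43–45 pregnancies in 76 women (57–59%), a rate found nowhere in the documents. The within-stratum figures above are the relevant ones.

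**Groups of 14 to 30 cannot carry covariates.** This has force against separate models, which have about 11–31 events per comparison in the simulations. It has much less against two covariates shared over 182 women.

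**The end point itself is undefined.** This is true and more serious: time origin, censoring and analysis set are all open. Fertility treatment starts only after complete response, so an analysis restricted to responders would shrink the groups and lose the protection of randomisation. Covariates do not cure that.

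**Conclusion.** The point holds as a minor, low-cost improvement. The plan names no baseline adjustment for one of its primary end points, two candidate covariates are available before randomisation, and neither is balanced by design. Gaps of 20 points in a common factor are to be expected in roughly one comparison in six (30 per group) to one in three (14 per group), assuming half the women hold it. The consequence is extra chance variation and some lost power; bias and an inflated type I error do not follow. At a treatment hazard ratio of 2 the average within-stratum gain is about 0–5 points across the assumed covariate strengths. Most contrasts remain below 0.5, so adjustment neither restores the stated 0.8 nor makes up for the missing effect-size justification.

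**What to change.** In III.3, before any outcome data are examined, specify for time to pregnancy and time to live birth:

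- all randomised women as the analysis set;
- one Cox model stratified by the four randomisation strata (disease by contraindication), with treatment terms within stratum;
- two fixed covariates shared across strata: age (continuous) and history of infertility (yes/no), with no data-driven selection;
- the unadjusted result reported beside the adjusted one.

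Time origin and censoring must be stated in the same paragraph for the model to be usable.

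The cost is a few lines of text and a little more analysis, with no new data. There are three small downsides. Covariate effects are assumed common to the strata. The assisted-reproduction rule may dilute the infertility effect. The adjusted hazard ratio is conditional on the covariates, so it differs from the unadjusted one even without imbalance, and the text should say that the two are not directly comparable.
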